### **10.3 HANDLING OF PATIENT TEMPORARY OR PERMANENT TREATMENT DISCONTINUATION AND OF PATIENT STUDY DISCONTINUATION**

The IMP should be continued whenever possible. In case the IMP is stopped, it should be determined whether the stop can be made temporarily; permanent IMP discontinuation should be a last resort. Any IMP discontinuation should be fully documented in the e-CRF. In any case, the patient should remain in the study and followed for the remainder of the study to collect vital safety status and endpoint data.

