#### **10.3.4 Handling of patients after permanent treatment discontinuation**

Every effort should be made to maintain patients in the study. Patients should be followed up according to the study procedures as specified in this protocol up to the scheduled date of study completion, or up to recovery or stabilization of any AE to be followed up as specified in this protocol, whichever comes later.

If a patient decides to discontinue study treatment early, a Premature EOT Visit (see [Section 10.1.3.2](#)) should be scheduled prior to treatment discontinuation, if possible. If not possible, the Premature EOT should be scheduled as soon as possible after treatment discontinuation. In the case of early discontinuation, no sample for measuring plasma concentration should be taken at the Premature EOT Visit, or at any subsequent visits. For patients who discontinue treatment but remain in the study, the remaining study visits should occur as scheduled where possible. The IRT should be notified of EOT.

All cases of permanent treatment discontinuation should be recorded by the Investigator in the appropriate pages of the e-CRF.

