2.1.4 Safety endpoints

The safety analysis will be based on the reported adverse events, hypoglycemia, acute renal failure, and other safety information, such as clinical laboratory data, vital signs, electrocardiogram (ECG), bone mineral density (BMD) results, physical examination, and marker of intestinal transit and absorption, markers of bone and calcium metabolism, etc.

Observation period

The observation period will be divided into 4 epochs:

- The **screening** epoch is defined as the time from the signed informed consent date up to the first administration of the double-blind IMP.
- The **treatment** epoch is defined as the time from the first administration of the double-blind IMP to the last administration of the double-blind IMP. This epoch includes the 26-week double-blind core treatment period and the 26-week double-blind extension treatment period. The 26-week core treatment period is the time from the first administration of double-blind IMP to the last administration of double-blind IMP on or before Visit 9/Week 26 (or Day 182 if Visit 9/Week 26 date is missing).
- The **residual treatment** epoch is defined as the time from the last administration of the double-blind IMP up to 10 days (1 day for hypoglycemia) after the last administration of the double-blind IMP.

The treatment-emergent adverse event (TEAE) period will include both **treatment** and **residual treatment** epochs (See TEAE period for the 26-week core treatment period in [Section 2.5.4](#)).

- The **posttreatment** epoch is defined as the period of time starting the day after the end of the treatment-emergent adverse event period up to the last protocol-planned visit or the

resolution/stabilization of all serious adverse events (SAE), adverse events of special interest (AESI) and events of special interest (EOSI), whichever is later.

The on-study observation period is defined as the time from start of double-blind treatment until the end of the study (defined as the last scheduled visit for those who completed the study and the date collected on e-CRF page “Completion of End of Study/Follow-up” for those who did not complete the study).

The post-study observation period is defined as the time from the day after the end of the study until the resolution/stabilization of all SAE, AESI and EOSI if applicable.

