Two independent committees will review safety events that require ongoing monitoring to ensure timing protocol amendments in case a safety signal is identified. These events are: 1) potential cases of drug-induced liver injury (DILI), and 2) cases of amputations. The two committees will review the cases in a treatment-blinded manner and will present their assessment to the DMC.

AESI and EOSI will be identified based on criteria in [Table 3](#).

Table 3 - Criteria for AESI and EOSI

AE Grouping	Criteria
AESI	
Pregnancy	eCRF "Pregnancy"
Symptomatic overdose with IMP/NIMP	"Overdose of IMP" or "Overdose of NIMP" checked and "Symptomatic overdose" checked in eCRF "Overdose"
ALT increase >3 X ULN	eCRF "ALT increase"
EOSI adjudicated	
Cardiovascular death	Positively adjudicated by CEC: "Cardiovascular" or "Undetermined" as the primary cause of death
Myocardial infarction, Unstable Angina requiring hospitalization	Positively adjudicated by CEC: Yes to the question "Does the event meet the definition of an MI for this study?", or Yes to the question "If event is not an MI, does the event meet the definition of an UA Requiring admission to hospital or emergency room, for this study?"
Stroke	Positively adjudicated by CEC: Yes to the question "Does the event meet the definition of a Stroke for this study?"
Heart failure requiring hospitalization	Positively adjudicated by CEC: Yes to the question "Does the event meet the definition of a Heart Failure Event for this study?"
Bone fractures	Positively adjudicated by CEC: Yes to the question "Did the Fracture occur?"
Diabetic ketoacidosis	Positively adjudicated by CEC: Yes to the question "Does this event meet the criteria to be a DKA event?"
EOSI Renal events where select events adjudicated	
Sustained ≥50% decrease in eGFR	(1) For ≥50% decrease in eGFR from baseline, (1a) confirmed ≥50% decrease in GFR for ≥30 days with no reversible cause as recorded in eCRF "eGFR decrease", OR (1b) positively adjudicated by CEC: Yes to the question "Does the subject meet the criteria of CKD progression".

Statistical Analysis Plan

Version: Final 3.0
Lexicon Pharmaceuticals Protocol No. EFC14837

Date of Issue: 21 November 2019
Covance Study ID:000000155205

AE Grouping	Criteria

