2.4.5 Analyses of safety data

The summary of safety results will be presented by treatment group. The safety data will be summarized for the 26-week core treatment period and the 52-week entire treatment period separately, unless otherwise specified.

The observation period defined in [Section 2.1.4](#) is applicable in all safety analyses for classification of AEs, determination of treatment-emergent Potentially Clinically Significant Abnormality (PCSA) values and the last on-treatment value for laboratory, vital sign, BMD and ECG.

General common rules

All safety analyses will be performed on the safety population as defined in [Section 2.3.2](#), unless otherwise specified, using the following common rules:

- Safety data in patients who do not belong to the safety population (eg, exposed but not randomized) will be listed separately.
- The baseline value (with the exception of serum creatinine and eGFR) is defined as the last available value before the first dose of double-blind IMP. For creatinine and eGFR, the baseline value is defined as the average of all values before the first dose of double-blind IMP.
- PCSA values are defined as abnormal values considered medically important by the Sponsor according to predefined criteria/thresholds based on literature review and defined by the Sponsor for clinical laboratory tests, vital signs, and ECG ([Appendix A](#)).
- PCSA criteria will determine which patients had at least 1 PCSA during the TEAE period, taking into account all evaluations performed during the TEAE period, including nonscheduled or repeated evaluations. The number of all such patients will be the numerator for the treatment-emergent PCSA percentage.
- The treatment-emergent PCSA denominator by group for a given parameter will be based on the number of patients assessed for that given parameter in the TEAE period by treatment group on the safety population.
- For laboratory parameters cited in the protocol as efficacy endpoints (eg, HbA1c, plasma glucose, etc.), PCSA summaries will not be provided. These parameters will be summarized in efficacy [Section 2.4.4](#).

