- TEAEs (PTs with incidence $\geq 5\%$ in any treatment group) by primary SOC, HLGT, HLT and PT, sorted by the internationally agreed SOC order. The other levels (HLGT, HLT, PT) will be presented in alphabetical order.
- Acute renal failure (narrow search on “Acute renal failure (SMQ)” [20000003]) by PT.

Analysis of all treatment emergent serious adverse event(s)

- All treatment-emergent serious adverse events by primary SOC, HLGT, HLT, and PT, showing the number (%) of patients with at least 1 serious treatment-emergent adverse event, sorted by the internationally agreed SOC order. The other levels (HLGT, HLT, PT) will be presented in alphabetical order.
- All treatment-emergent serious adverse events regardless of relationship and related to IMP, by primary SOC, HLGT, HLT, and PT, showing the number (%) of patients with at

least 1 treatment-emergent serious adverse event, sorted by the internationally agreed SOC order. The other levels (HLGT, HLT, PT) will be presented in alphabetical order.

Analysis of all treatment-emergent adverse event(s) leading to treatment discontinuation

- All treatment-emergent adverse events leading to treatment discontinuation, by primary SOC, HLGT, HLT, and PT, showing the number (%) of patients sorted by the internationally agreed SOC order. The other levels (HLGT, HLT, PT) will be presented in alphabetical order.

Analysis of adverse events of special interest

The summaries of AESI will be presented for the 52-week entire treatment period only in the safety population.

Pregnancy and overdose will be included in overall AE summaries if any are reported. ALT increase >3 x ULN is included in laboratory PCSA summary if any.

In addition, the number (%) of patients with an AESI will be summarized by PT and by treatment group. Corresponding listings will be provided as appropriately.

Analysis of events of special interest

The summaries of EOSI will be presented for the 52-week entire treatment period only in the safety population.

CV events, bone fracture and DKA

For EOSIs that are adjudicated (ie, deaths, myocardial infarction, stroke, and unstable angina requiring hospitalization, heart failure requiring hospitalization, bone fracture, and diabetic ketoacidosis), the number (%) of patients with an EOSI positively adjudicated by CEC will be summarized by treatment group. All EOSIs sent for adjudication and/or reported by the Investigators in the specific AE forms will be listed along with the adjudication outcome.

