Renal events

For the EOSI renal events where selected events are adjudicated, the number (%) of patients with any renal events identified in [Table 3](#) in [Section 2.1.4.2](#) will be summarized by treatment group.

The following renal events will be listed along with the adjudication outcome if applicable, including events,

1. Recorded in eCRF “GFR decrease”.
2. Recorded in eCRF “Renal Event - Dialysis”.
3. Identified as “Renal transplant” in eCRF “Other procedure”.

Renal death will be part of all deaths specified above.

Other EOSIs

For EOSIs that are not adjudicated, the number (%) of patients with at least one event will be summarized by treatment group and by PT (as identified in [Table 3](#) in [Section 2.1.4.2](#)).

Severe hypoglycemia will be included in the summary of hypoglycemia (See [Section 2.4.5.1](#)).

AE leading to an amputation is described in the section below.

Analysis of Amputation

The number (%) of patients with amputation will be summarized by treatment group and by PT and LLT during the study (ie, regardless of on- or post-treatment). Amputation is a procedure recorded in eCRF “Other Procedures related to Amputation”. Patients who had a procedure related to amputation will be listed.

The number (%) of patients with an “AE leading to an amputation” will be summarized by treatment group and by PT. The “AE leading to an amputation” is determined by the AE identifier recorded in eCRF “Other Procedures related to Amputation” when “AE correction” is chosen as the reason for the amputation procedure.

In addition, the number (%) of patients with an “AE potentially leading to an amputation” will be summarized by treatment group and by PT (as identified in [Table 3](#) in [Section 2.1.4.2](#)); these PTs in [Table 3](#) were requested by the European Medicines Agency/Pharmacovigilance Risk Assessment Committee [EMA/PRAC] Assessment Report 9 February 2017). The associated list will be provided as well, with patients who had an amputation procedure flagged. “AE potentially leading to an amputation” represents the condition that may potentially lead to the amputation procedure, but not in all cases an amputation has occurred (as per the EMA/PRAC request).

Analysis of pretreatment and posttreatment adverse events

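### Events of special interest are counted by arm only to last dose plus 10 days although patients are followed to study end, so an on-study count by arm is missing

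*SAP*

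**What the plan says.** On the window, SAP 2.4.5.2 states: "The summaries of EOSI will be presented for the 52-week entire treatment period only in the safety population". The default it departs from is in SAP 2.4.5: "The safety data will be summarized for the 26-week core treatment period and the 52-week entire treatment period separately, unless otherwise specified". SAP 2.4.5 also says that the observation period defined in SAP 2.1.4 "is applicable in all safety analyses for classification of AEs". Under SAP 2.1.4 the treatment-emergent period is the treatment epoch, first to last administration, plus a residual epoch running "up to 10 days (1 day for hypoglycemia) after the last administration of the double-blind IMP".

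On follow-up, Protocol 10.3 asks that, whatever the reason for stopping IMP, "the patient should remain in the study and followed for the remainder of the study to collect vital safety status and endpoint data". Protocol 10.3.4 repeats it: "Patients should be followed up according to the study procedures as specified in this protocol up to the scheduled date of study completion".

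Elsewhere the SAP uses a wider window. Amputation, also in 2.4.5.2, is summarised "by PT and LLT during the study (ie, regardless of on- or post-treatment". BMD (2.4.5.8) is analysed whether or not IMP was stopped. Deaths (2.4.5.3) are tabulated on-study as well as on-treatment.

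**The concern.** The trial pays for follow-up after IMP is stopped, and a committee adjudicates cardiovascular events, fracture, DKA and selected renal events. The by-arm summary of those events then ends shortly after last dose. Patients who stop are not a random subset, and stopping may differ by arm, so a cut-off tied to last dose can be informative. The risk is greatest for outcomes that take time to appear, such as malignancy and fracture, and for renal criteria that need confirmation over weeks. Protocol 4.4 does not expect clinical outcomes at a high rate, so leaving out even a few events could change how the arms compare.

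**Working it through.** The plan states no figure on this point, so there is nothing to reproduce. The check is a comparison of windows, followed by arithmetic on how much follow-up each window covers.

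**1. What the word 'only' removes.** Set against the SAP 2.4.5 default, it removes the separate 26-week table. What remains is still a treatment period. I read it as including the 10 residual days, which is the more generous reading. That amputation and BMD needed express wording supports this.

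**2. Which outputs reach study end.**

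| Outcome | By-arm output beyond last dose + 10 days |
|---|---|
| Death, all causes | Yes, on-study (SAP 2.4.5.3) |
| Amputation; BMD | Yes (2.4.5.2; 2.4.5.8) |
| ESRD; >50% eGFR decline | Yes, ITT, censored at end of study (2.4.4.3, Table 5, Appendix D) |
| Adjudicated MI, stroke, unstable angina, heart failure, fracture, DKA | No adjudicated count; events sent for adjudication are listed |
| CV death as a MACE component | No; the death table by period is all-cause |
| Table 3 renal events | No |
| Grouped venous thrombotic events and malignancies | No grouped count |

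**3. Can existing tables be combined?** The post-treatment AE table in 2.4.5.2 gives investigator-reported terms by SOC and PT, without the adjudication outcome or the Table 3 grouping. A patient is counted once per event within each treatment phase, so someone with events in both phases appears in both tables. Adding the two does not give patients with an event.

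**4. Renal confirmation.** Table 3 accepts a confirmed decrease "in GFR for ≥30 days with no reversible cause as recorded in eCRF", or dialysis lasting at least 90 days, or CEC adjudication instead. Both durations exceed the 10-day tail. The SAP does not say whether the onset date or the confirmation date places a Table 3 renal event in a period.

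**5. Share of follow-up outside the window.** Observed days are 364 + 28 = 392 (flow chart, Visit 12). For a permanent stop on Day t, days outside = 392 − t − 10.

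- Day 28: 354 days (90%)
- Day 84: 298 days (76%)
- Day 182: 200 days (51%)
- Day 273: 109 days (28%)
- Completer (t = 364): 18 days (4.6%)

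The documents give no discontinuation rate. As an assumption, let a fraction p stop, uniformly over Days 1 to 364 (mean 182.5), with everyone followed to Day 392. The average number of days outside is p × (392 − 182.5 − 10) + (1 − p) × 18 = 199.5p + 18(1 − p).

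- p = 5%: 27.1 days, 6.9%, about 19 patient-years per arm of 260
- p = 10%: 36.2 days, 9.2%, about 26
- p = 20%: 54.3 days, 13.9%, about 39
- p = 30%: 72.5 days, 18.5%, about 52

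The total is 260 × 392 / 365.25 = 279 patient-years per arm. Of each percentage, 4.6 points are the routine follow-up tail that would exist with no discontinuation. The part due to stopping is therefore 2.3 to 13.9 points. If early stoppers are followed only to Day 364, a Day 182 stop leaves 364 − 182 − 10 = 172 of 364 days (47%) outside.

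**The case against.** Much of the case against a broader claim is right.

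- **Stop-triggering events.** A reader might infer that events causing IMP to be stopped drop out. In general they do not. Such an event normally starts on treatment, so it is treatment-emergent and counted, and AEs leading to discontinuation have their own table.
- **Late events.** A reader might infer that they are visible only in listings. Investigator-reported ones are tabulated by SOC and PT, with safety results presented by arm. Only the adjudicated or grouped count is missing.
- **Renal outcomes.** They are not lost. ESRD and >50% eGFR decline run to study end in ITT.
- **The creatinine rule.** A reader might argue that it always stops IMP before the eGFR criterion can be met, since a 50% creatinine rise gives 1.5^−1.154 = 0.626, a 37% eGFR fall. That fits only the comparison with Baseline, used up to Week 8. Afterwards Protocol 10.6.2 compares with the last two visits. Creatinine of 1.0, 1.3, 1.6 and 1.9 at successive visits (preceded by values near 1.0) never exceeds 1.5 times the two-visit mean, yet passes the 1.82-fold rise that halves eGFR. The stop is also first a 2-week interruption, and a patient who restarts stays in the window.
- **Mismatched renal counts.** The EOSI and efficacy renal counts will differ anyway, because one uses a sustained or adjudicated ≥50% decrease in the safety population and the other >50% in ITT. An on-study table does not cure that.

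Safety is descriptive, TEAEs are the stated focus, and the 10-day tail is justified by half-life. These are good reasons to keep the on-treatment table. They are not reasons to omit the on-study one for outcomes that the trial follows and adjudicates after IMP is stopped.

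**Conclusion.** The point holds in limited form. Adjudicated non-fatal cardiovascular events, cardiovascular death within MACE, fracture and DKA, the Table 3 renal events, and grouped venous thrombotic events and malignancies have no by-arm count over the period for which patients are followed. The renal gap is confined to the Table 3 composite, whose ≥30-day or ≥90-day confirmation can fall beyond the 10-day tail after a permanent stop.

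The 7% to 18% of person-time is illustrative: it rests on an assumed 5% to 30% discontinuation at uniform times with full retention. No event count or arm difference is shown to change, and no power or alpha figure is affected. The change is worth making because the missing summary is more complete, less exposed to an informative cut-off, and cheap.

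**What to change.** In SAP 2.4.5.2, keep the on-treatment EOSI table and add beside it number (%) of patients by arm over the on-study observation period that SAP 2.1.4 already defines (first dose to end of study), regardless of IMP discontinuation. Cover CEC-adjudicated cardiovascular events including cardiovascular death, fracture and DKA; the Table 3 renal events; venous thrombotic events; and malignancies (which are not adjudicated).

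State that an event is assigned to a period by its onset date, including renal events confirmed later. Because SAP 1.6 records that the first-step analysis has already been conducted and reported for top-line results, label the table as added after those results.

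The cost is SAP wording and one set of descriptive tables from data already collected and, where applicable, adjudicated. The downside is that on-study counts include events remote from exposure; the retained on-treatment table separates these.

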2.4.5.3 Deaths

The following summaries of deaths will be generated.

- Number (%) of patients who died by study period (on-study, on-treatment, post-study).
- Deaths in nonrandomized patients or randomized but not treated patients.
- Treatment-emergent adverse events leading to death (death as an outcome on the adverse event case report form page as reported by the Investigator) by primary SOC , HLGT, HLT, and PT showing number (%) of patients sorted by internationally agreed SOC order, with HLGT, HLT, and PT presented in alphabetical order within each SOC .

2.4.5.4 Analyses of laboratory variables

Laboratory parameters will be grouped and summarized by biological function as described in [Section 2.1.4.4](#).

The summary statistics (including number, mean, median, Q1, Q3, standard deviation, minimum and maximum) of all laboratory variables (central laboratory values, changes from baseline, and/or percent change from baseline [eg, lipid parameters, albumin, total protein, hemoglobin, hematocrit]) will be calculated for each applicable visit or study assessment (screening, baseline, post-baseline time point, last on-treatment value) by treatment group. Graphical presentations may be used to examine trends over time using mean (\pm SE) and/or mean change from baseline (\pm SE) at scheduled visits (eg, creatinine, eGFR).

The incidence of PCSAs (list provided in Appendix A) at any time during the treatment-emergent adverse event period will be summarized by biological function and treatment group whatever the baseline level and/or according to the following baseline status categories:

- Normal/missing.
- Abnormal according to PCSA criterion or criteria.

For creatinine, $\geq 50\%$ change from baseline will be provided in addition to the PCSA criteria defined, ie, $\geq 150 \mu\text{mol/L}$ (Adults), $\geq 30\%$ change from baseline, $\geq 50\%$ change from baseline, and $\geq 100\%$ change from baseline will be presented. For eGFR, $\geq 50\%$ decrease from baseline will be provided in addition to the PCSA criteria defined, ie, < 15 (end stage renal disease), $\geq 15 - < 30$ (severe decrease in GFR), $\geq 30 - < 60$ (moderate decrease in GFR), $\geq 60 - < 90$ (mild decrease in GFR), and $\geq 50\%$ decrease from baseline will be presented. For parameters for which no PCSA criteria are defined, similar table(s) using the normal range will be provided.

All measurements collected during the TEAE period, including values from unscheduled visits, will be considered for the PCSA summaries. The summary tables will include patients in the safety population that have at least 1 assessment performed during the TEAE period. When a PCSA definition involves a change from baseline value, patients must also have a baseline value to be included in the summaries, and when required by the definition of the abnormality, patients must also have available laboratory normal ranges.

A listing of patients with at least 1 post-baseline measurement PCSA or out of normal range (when no PCSA is defined) will be provided and will display the patients' entire profile over time for parameters belonging to the corresponding biological function. Individual data listings will include flags when applicable:

- Baseline values will be flagged "B".
- Normal laboratory ranges, available for most laboratory parameters, will be identified as ULN and LLN. Baseline, last on-treatment value, and individual data will be flagged "L" if the value is below the LLN and will be flagged "H" if it is above the ULN.
- Laboratory PCSA criteria will be used for the corresponding laboratory parameters. Values reaching a PCSA limit will be flagged (+, ++, -, or -- depending upon the direction and level of the abnormality). Flags for WBC and differential counts will be determined using data expressed in international units.

For parameters whose PCSA criteria are based on multiples of ULN, the parameter's value will also be expressed as multiples of ULN in the individual data presented.

Drug-induced liver injury

The liver function tests, namely AST, ALT, alkaline phosphatase, and total bilirubin, are used to assess possible drug-induced liver toxicity. The proportion of patients with PCSA values at any post-baseline visit by baseline status will be displayed by treatment group for each parameter. The proportion of patients with PCSA values at any post-baseline visit will also be displayed by duration of exposure for each treatment group (only if a tabulation summary is necessary).

Listing of possible Hy's law cases identified by treatment group (eg, patients with any elevated $\text{ALT} > 3 \times \text{ULN}$, and associated with an increase in bilirubin $\geq 2 \times \text{ULN}$) with ALT, AST, alkaline phosphatase, total bilirubin, and the following complementary parameters if available: conjugated bilirubin and prothrombin time/international normalized ratio, creatine phosphokinase, serum creatinine, complete blood count, anti-HAV IgM, anti-HBc IgM, anti-HCV and HCV RNA,

anti-CMV IgM and anti-HEV IgM antibodies, auto-antibodies: anti-nuclear, anti-DNA, anti-smooth muscle, Epstein-Barr virus, herpes viruses, and anti-LKM.

